    - Are  $\geq$  50 years of age, quit smoking but have smoked within the past 15 years, and have a  $\geq$  30 pack-year history.If the test results are negative for lung cancer, the Participant will be allowed to enter the study.
  - **Prostate-specific antigen (PSA) test** for prostate cancer, if not performed within the past 12 months, for male Participants who are African-American aged  $\geq$  45 years or other races aged  $\geq$  50 years. If the test results are negative for prostate cancer, the Participant will be allowed to enter the study.
8. **Retinal Fundoscopy** will be performed by an ophthalmologist or optometrist at Screening, up to 45 days before the Day 90 Visit (pre-dose), and up to 30 days before the Day 180 Visit (and, if possible, upon Early Termination if the Participant discontinues after the Day 90 Visit). If the retinal funduscopy results at Screening are deemed insufficient to determine eligibility, fluorescein angiography may need to be performed. Results of the funduscopy examinations at Days 90 and 180 compared to results at Screening will be assessed by the Investigator.
9. **12-Lead Electrocardiogram (ECG)** will be performed at Screening, pre-dose on Day 90, and on Day 180. Any clinically significant findings at Screening will be recorded as part of medical history. Clinically significant abnormalities are to be recorded as adverse events, except at Screening. The ECG recording and interpretation will be printed out and stored with the Participant's records.

10. **Ultrasound** of the right and left gastrocnemius muscles of the calf will be used to measure the depth to the muscles and width of the muscles at Screening in preparation for the IM injections of the study drug.
11. **Serum Chemistry, Hematology, and Lipid Profile:** These laboratory assessments will be evaluated at Screening to establish eligibility and baseline measurements for comparison with assessments on Days 0, 90, and 180.
  - **Chemistry** includes sodium, potassium, chloride, bicarbonate, calcium, inorganic phosphate, magnesium, glucose, amylase, lipase, creatine kinase, lactate dehydrogenase, and
    - Kidney function tests (blood urea nitrogen, creatinine)
    - Liver function tests (aspartate aminotransferase [AST], alanine aminotransferase [ALT], alkaline phosphatase, gamma-glutamyl transpeptidase [GGT], total bilirubin, total protein, and albumin)
    - Cystatin C (at Screening to calculate eGFR)

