**Table 1 Potential Risks of Clinical Significance**

Potential Risk of Clinical Significance	Summary of Data/Rationale for Risk	Mitigation Strategy
Risks of Engensis		
Eye disorders	Eye disorders were observed in both Engensis and Placebo Participants, including diabetic retinopathy, which was observed at a higher incidence in the Placebo arm.	Presence of TEAEs will be assessed pre- and post-dose on Days 0, 14, 90, and 104, as well as Days 28, 60, 150, and 180 to detect new or worsening prior eye disorders.  Retinal fundoscopic examinations will be performed at Screening and Days 90 and 180.

Potential Risk of Clinical Significance	Summary of Data/Rationale for Risk	Mitigation Strategy
Angiogenesis and promotion of tumor growth (cancer)	Because HGF has the potential to create new blood vessels (angiogenesis), there may be a risk of promoting tumor growth (cancer).	During Screening, all Participants will undergo cancer screening to minimize randomizing patients at increased risk for cancer or who have subclinical (no overt signs or symptoms) cancer.  In addition, Participants who have two or more first- degree relatives with breast, cervical, colon, endometrial, or prostate cancer will be excluded to minimize risk of cancer during the study.
	Hyperplasia of the vasa vasorum in the early stages of atherosclerosis is independent of angiogenesis, but the intimal neovascularization that follows the hyperplasia of the vasa vasorum is angiogenesis-dependent.	During Screening, Participants diagnosed to have had a cerebrovascular accident or myocardial infarction within 3 months before Screening will be excluded in addition to Participants with Class 3 or 4 heart failure.
Risks of Study Procedures		

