### 6.1.3. Summary of Study Intervention Characteristics

Study Arm	Engensis	Placebo
Study Drug	Engensis	Placebo
Type	Biologic	N/A
Formulation	Lyophilized product to be reconstituted	Injectable liquid
Amount of Active Drug	2.5 mg Engensis per vial	N/A
Dosage Level per Treatment Cycle	Total of 16 mg per Treatment Cycle, with each cycle composed of 2 days of 16 injections each to the right and left gastrocnemius muscles, spaced 2 weeks apart	Each Treatment Cycle composed of 2 days of 16 injections each to the right and left gastrocnemius muscles, spaced 2 weeks apart
Route of Administration	IM injection	IM injection
Use	Experimental	Placebo
Sourcing	Provided centrally by the Sponsor	Provided centrally by the Sponsor
Packaging and Labeling	Engensis will be provided in a vial. Each vial will be labeled per country requirement.	Placebo will be provided in a vial. Each vial will be labeled per country requirement.
Former Names	VM202	N/A

Abbreviations: IM = intramuscular; N/A = not applicable

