### **7.2. Participant Discontinuation/Withdrawal/Early Termination from the Study**

Any Participant may voluntarily discontinue the study at any time without prejudice. The Investigator may discontinue a Participant from the study at any time if, in the Investigator's judgment, the Participant's health or safety would be compromised by remaining in the study.

Specific reasons for study discontinuation include the following:

- Participant's decision
- Investigator's decision
- Adverse event
- Insufficient compliance with study requirements
- Lost to follow-up
- Other

The specific reasons for Participant discontinuation will be recorded.

The following assessments will be performed, if possible, for Participants who discontinue prior to the Day 180 Visit, at the Early Termination Visit (ET; see Section 1.3, SoA).

- APR and PRR
- Full BPI-DPN
- MNSI
- BST
- PGIC
- SF-36 and EQ-5D
- Complete physical examination
- Vital signs, weight
- Retinal fundoscopy
- Serum chemistry, lipid profile, and hematology
- ECG
- Urine pregnancy test
- Urine drug analysis
- HbA1c

- Concomitant medications / procedures
- Adverse events
- Anti-HGF antibodies

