## 8. STUDY ASSESSMENTS AND PROCEDURES

Study procedures and their timing are summarized in Section 1.3 (SoA).

Protocol waivers or exemptions are not allowed. Adherence to the protocol requirements, including those specified in the SoA, is essential.

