#### **8.4.7. Retinal Fundoscopy**

Proliferative diabetic retinopathy, defined as the presence of new proliferating blood vessels (neovascularization) arising from the retina or optic disc and growing on the retinal surface or into the vitreous cavity, will be assessed by retinal funduscopy during Screening for eligibility and repeated at Day 90 and Day 180/Early Termination. Retinal funduscopy must be performed

by an ophthalmologist or optometrist within 52 days prior to Day 0 and within 45 days of Day 90, and within 30 days of Day 180. The same ophthalmology practice should be used for all measurements of individual participation. In cases where fundoscopy alone is deemed insufficient to determine eligibility, fluorescein angiography may be performed during Screening.

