##### Proliferative diabetic retinopathy

Neovascularization is an advanced stage of diabetic retinopathy that is due to relentless abnormal fibrovascular proliferation. Because the angiogenic potential of Engensis may promote the development of or stimulate abnormal fibrovascular proliferation in the retina, new fundoscopic changes or symptoms of proliferative diabetic retinopathy that occur after Baseline are considered AESIs.

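### Footnote 8 of the Schedule of Activities drops the early-termination retinal exam for participants who leave before the Day 90 Visit, in conflict with Protocol 7.2 and 8.4.7

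*Protocol*

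**What the plan says.** Four places in the protocol deal with fundoscopy at early termination.

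- **Section 1.3, footnote 8.** The exam is done at Screening, before the Day 90 Visit and before the Day 180 Visit. At early termination it is conditional: "if possible, upon Early Termination if the Participant discontinues after the Day 90 Visit". The Day 90 exam has a wide window: "up to 45 days before the Day 90 Visit (pre-dose").
- **Section 1.3, grid.** The fundoscopy row is marked in the final column, which serves both Day 180 and early termination.
- **Section 7.2.** "The following assessments will be performed, if possible, for Participants who discontinue prior to the Day 180 Visit". Retinal fundoscopy is on the list that follows, with no qualifier of its own. The section refers to the Schedule of Activities for the early-termination visit.
- **Section 8.4.7.** The exam is "repeated at Day 90 and Day 180/Early Termination", with neither a Day 90 condition nor a best-effort qualifier.

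Section 8 adds: "Adherence to the protocol requirements, including those specified in the SoA, is essential". On purpose, Section 8.5.4.1 states that "new fundoscopic changes or symptoms of proliferative diabetic retinopathy that occur after Baseline are considered AESIs", and Table 1 in Section 2.3.1 lists fundoscopy as a mitigation for eye disorders: "Retinal fundoscopic examinations will be performed at Screening and Days 90 and 180".

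**The concern.** The footnote and the two body sections give different instructions for the same participant: someone who has been injected and withdraws before the Day 90 Visit. Under 7.2 and 8.4.7 that person is due a retinal exam on leaving; under footnote 8 that person is not. Two sites can treat identical leavers differently and each point to the protocol.

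The condition also falls on the wrong group. Those who leave after the Day 90 Visit should already have one post-dose exam. Those who leave before it may have none, and they are the ones from whom the footnote stops asking for it.

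At stake is the detection of a retinal event that the protocol itself ties to the product's angiogenic potential. A new fundoscopic change without symptoms can only be found by looking. Early leavers still get adverse event questioning and a physical examination that includes the eyes, but neither replaces fundoscopy by an ophthalmologist or optometrist. These participants are in the Safety Population after a single injection, so they would be counted there with a baseline retinal finding and no follow-up finding.

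**Working it through.** The plan states no figure on this point. The check is a comparison of texts plus simple arithmetic on days and dose.

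**Inputs**

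- Injection visits: Days 0, 14, 90 and 104 (Protocol 4.1).
- Dose: 8 mg per injection visit, both legs together (Protocol Tables 2 and 3). Section 6.1.3 gives the same sum per cycle: "Total of 16 mg per Treatment Cycle". The overall dose is 32 mg (Protocol 4.4).
- Window of the first post-dose exam: up to 45 days before the Day 90 Visit (footnote 8).
- Follow-up: 180 days.

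**Step 1. When can the first scheduled post-dose exam take place?** 90 − 45 = Day 45 at the earliest, taking the Day 90 Visit at its nominal date.

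**Step 2. What does each rule give a leaver?**

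| Time of leaving | Scheduled post-dose exam already done? | Exam at early termination, footnote 8 | Exam at early termination, 7.2 and 8.4.7 |
|---|---|---|---|
| After first dose, before about Day 45 | No | Not requested | Yes (7.2: if possible) |
| About Day 45 to the Day 90 Visit | Only if the Day 90 exam was done early | Not requested | Yes (7.2: if possible) |
| After the Day 90 Visit | Yes, the Day 90 exam, if done as scheduled | Yes, if possible | Yes (7.2: if possible) |

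**Step 3. How long is the gap?**

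- Shortest, with the exam done as soon as the window opens: 45 / 180 = 25% of follow-up.
- Longest, with the exam done at the Day 90 Visit itself: 90 / 180 = 50% of follow-up.

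**Step 4. How much drug has been given by then?** By Day 45, two of four injection visits: 2 × 8 mg = 16 mg, and 16 / 32 = 50% of the planned dose in the Engensis arm.

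**Step 5. Does anything settle the conflict?** Section 7.2 refers to the Schedule of Activities, which could be read as giving way to the footnote. Section 8.4.7 contains no such reference. Section 8 demands adherence to the protocol and to the Schedule alike and ranks neither above the other. The conflict stands in current text.

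**The case against.** The strongest case on the other side has four parts.

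- **The gap depends on how the footnote is read.** The footnote forbids nothing, the grid marks the exam in the shared early-termination column, and a site that follows 7.2 and 8.4.7 will examine every leaver. This is true, but the footnote is the most specific instruction on timing, and a site that applies it is not in breach.
- **The limit may be deliberate.** The Day 90 exam is taken before the Day 90 injections. A participant who leaves after them has received 16 + 8 = 24 mg, or 32 mg after Day 104, and would otherwise have no exam after that exposure. So the exam for later leavers is not redundant. That is a sound reason to keep it for them. It is not a reason to omit it for dosed participants who have had no post-dose exam, and the protocol gives no rationale for doing so.
- **Other safeguards exist.** Proliferative retinopathy is excluded at entry (exclusion criterion 14). Participants who only stop study drug can stay in the study for safety evaluation (Section 7.1). Symptoms also count towards the event of special interest, and such events are followed up. Table 1 reports more diabetic retinopathy on placebo than on Engensis in earlier experience. All of this stands. It narrows the gap to retinal change without symptoms in participants who withdraw fully before a Day 90 exam, and it means the issue is ascertainment, not a demonstrated signal.
- **The size is in calendar time.** The 25% and 50% are shares of follow-up, not of participants or missed events. This is correct, and the documents do not allow better. Participants lost to follow-up cannot be examined under any wording.

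**Conclusion.** The concern holds. Footnote 8 contradicts 7.2 and 8.4.7. A site that applies it can release a participant who has received 16 of 32 mg of Engensis with no retinal exam since dosing. The gap covers about the first 45 days of follow-up at the least and 90 days at the most.

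This rests on nominal visit days and on the site treating the footnote as the governing instruction. The count of affected participants is unknown. The consequence is confined to individual safety monitoring: SAP 8.5.8 summarises fundoscopy descriptively, and the primary endpoint, power and type I error do not depend on it. It should be corrected, but it does not threaten the trial's main conclusion.

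**What to change.** In footnote 8, delete the clause that limits the early-termination exam to those who leave after the Day 90 Visit, and keep the words that ask for the exam at early termination if possible. The rule is then the one in 7.2: whenever a dosed participant leaves before Day 180, an exam is sought. Participants who leave after Day 90 keep theirs. In the same edit, the best-effort qualifier could be added to 8.4.7, which lacks it, so that all three places read alike.

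If the sponsor wants to avoid repeat exams within days of each other, the request can instead be limited to dosed participants with no recent post-dose exam, with the interval stated and the same text used in all three places.

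The cost is one clause in one footnote and an eye-clinic visit for each early leaver who can be examined, an exam that 7.2 and 8.4.7 already call for. Because the wording stays best-effort, the change makes an exam more likely but does not guarantee one.

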## 2. INTRODUCTION

Engensis is a novel gene therapy treatment being developed for the durable management of

### 2.1. Study Rationale

Diabetic peripheral neuropathy is a bilateral neuropathy. Based on the excellent safety profile of Engensis observed in the Phase 1 and Phase 2 critical limb ischemia (CLI) studies, preliminary efficacy data from the Phase 1/2 studies, safety data from the Phase 1/2 studies and the Phase 3 studies of Engensis in Participants with DPN, we propose continued bilateral treatment in this Phase 3 study.

The purpose of this study is to evaluate the efficacy and safety of IM administration of Engensis on pain in Participants with painful DPN in the feet and lower legs, as compared to Placebo, as a second well-controlled study sufficient to support the efficacy and safety of Engensis.

Engensis will be tested against Placebo. The total dose per Treatment Cycle of Engensis plasmid DNA delivered per leg will remain within the dosing scheme of the Phase 2 study and the prior Phase 3 DPN study (16 mg per leg, for a total of 32 mg per Participant). As was done in the prior Phase 3 study (Protocol VMDN-003), Participants will receive Engensis or Placebo by IM injections in the gastrocnemius muscles in both legs during two Treatment Cycles: Treatment Cycle 1, Day 0 and Day 14 (13 to 15 days after the Day 0 Visit) and Treatment Cycle 2, Day 90 and Day 104 (13 to 15 days after the Day 90 Visit).

As in all prior/ongoing studies, Engensis will be delivered as a solution containing 0.5 mg/mL of VM202. Participants will be treated with an overall final dose of 32 mg Engensis or Placebo, dosages well within those supported by the body of pharmacology and toxicology safety studies of Engensis.

## **2.2. Background**

[figure not shown]
### **2.2.1. Pathophysiology of Diabetic Peripheral Neuropathy**

Diabetic peripheral neuropathy (DPN) is a bilateral, particularly debilitating complication of diabetes characterized by pain that is burning, lancinating, tingling, or shooting (electric shock-like), occurring with paresthesia, and is typically worse at night. The pain can either be triggered by an external stimulus or be independent of external input. Unlike other painful sensations, which signal a warning in response to a harmful stimulus, neuropathic pain is maladaptive. Diabetic peripheral neuropathy accounts for significant morbidity by predisposing the foot to ulceration and lower extremity amputation.

Diabetic peripheral neuropathy manifests as three broad categories: sensory, motor, and autonomic, with the most prevalent form being somatic or sensorimotor neuropathy. Symptoms (e.g., burning, tingling, stabbing, or pins-and-needles) often exhibit a distal symmetric pattern, beginning at the base of the toes and ascending proximally up the lower leg as the disease progresses. Patients may also display muscle weakness, lack of coordination and ataxia, and loss of pain perception. Loss of protective sensation can lead to the formation of foot ulcerations, infections, and amputations.

The sequence of physiological events that result in DPN is poorly understood. The pathogenesis of diabetic neuropathy likely involves the interplay of hyperglycemia, ischemia, and oxidative stress. [Figure 1](#) portrays the relationship of hyperglycemia to oxidative stress, metabolic alterations, vascular dysfunction, and neural damage.

**Figure 1            The Neurodestructive Effects of Hyperglycemia**

***Increased polyol pathway flux.*** Hyperglycemia causes increased levels of intracellular glucose in nerves, leading to saturation of the glycolytic pathway. Extra glucose is shunted into the polyol pathway and converted to sorbitol and fructose by aldose reductase and sorbitol dehydrogenase, respectively. Accumulation of sorbitol and fructose leads to reduced nerve myoinositol, decreased membrane Na+/K+-ATPase activity, impaired axonal transport, and structural breakdown of nerves, causing abnormal action potential propagation.

***Non-enzymatic protein glycation.*** Advanced glycation end products occur because of nonenzymatic addition of glucose or other saccharides to proteins, lipids, and nucleotides. In diabetes, excess glucose accelerates advanced glycation end-product generation that leads to intracellular and extracellular protein cross-linking and protein aggregation. Activation of the advanced glycation end-product receptor alters intracellular signaling and gene expression, releases proinflammatory molecules, and results in an increased production of reactive oxygen species (ROS) that contribute to diabetic microvascular complications.

***Oxidative Stress.*** Glucose can cause significant oxidative stress and damage when present in excess. Under physiological conditions, aerobic respiration is associated with the formation of a small number of free radicals or ROS. In a hyperglycemic state, however, particularly in endothelial cells, which do not have the ability to limit glucose entry into the cell, glucose accumulation exceeds the levels that glycolytic enzymes can handle. The flood of excess glucose into endothelial cells is shunted into alternate metabolic pathways (e.g., polyol pathway, glycosylation, hexosamine pathway, the diacylglycerol activation of protein kinase C [PKC]). These pathways, particularly PKC, produce significantly larger amounts of ROS than aerobic respiration, overwhelming compensatory antioxidant mechanisms. The resulting hyperglycemic oxidative stress contributes to endothelial dysfunction by inhibiting endothelial nitric oxide production and by initiating and promoting the deposition of modified lipids in the subendothelium. These factors accelerate atherosclerotic macrovascular disease and are associated with the development of apoptosis in neurons and supporting glial cells.

***Vascular Damage.*** Nerve tissue depends on adequate blood flow to deliver nutrients and remove metabolic waste. Normally, the capillary basement membrane allows the passage of nutrients into the cell and permits the removal of waste products. In patients with prolonged hyperglycemia, glucose is more likely to be deposited in the basement membrane, thus decreasing its permeability. Decreased permeability results in the buildup of toxic metabolites, resulting in poor cellular metabolism, further free radical formation, apoptosis, and a decline in vascularization of nervous tissues.

### **2.2.2. Current Treatment Options**

Currently no approved drugs or interventional strategies are known to halt or reverse the progression of DPN. Treatments target pain reduction, physical function improvement, reduction of psychological distress, and quality of life improvements.

Long-term complications of both type 1 and type 2 diabetes can be reduced by tight glycemic control. To date, this is the only intervention specifically shown to arrest or postpone the onset and severity of peripheral neuropathy. The consequences of DPN can be ameliorated by the education of patients and their care providers as to foot care, proper footwear and of hyposensitive areas and pressure points, all to prevent the occurrence of ulcers and to lower the risk of infection of soft tissue and bone.

The incidence of neuropathy is also associated with potentially modifiable cardiovascular risk factors, including an elevated triglyceride level, a high body mass index (BMI), smoking, and hypertension.

Four drugs have been approved by the Food and Drug Administration (FDA) specifically for the treatment of the symptoms of DPN: Nucynta ER (tapentadol), an opioid medication; Cymbalta (duloxetine), a serotonin and norepinephrine reuptake inhibitor; Lyrica (pregabalin), an anticonvulsant drug; and Qutenza (capsaicin), a transdermal patch. All are prescribed for the management of pain associated with DPN.

See the IB for presentation of guidelines issued by international organizations for the use of agents to treat DPN.

Another treatment option is  $\alpha$ -lipoic acid, a naturally occurring antioxidant compound found in spinach and broccoli.  $\alpha$ -Lipoic acid was recently studied in a multicenter, placebo-controlled

study of Participants with type 2 diabetes and symptomatic neuropathy. One hundred eighty-one (181) Participants were given daily oral doses of 600, 1200, or 1800 mg of  $\alpha$ -lipoic acid or placebo. After 5 weeks, neuropathic symptoms improved in those Participants who received  $\alpha$ -lipoic acid. The 600-mg dose appeared to provide the optimum risk-to-benefit ratio.

There are also invasive treatment options. One option is surgical decompression of the lower-extremity peripheral nerves in patients with DPN but this is still considered an experimental intervention (see IB for details). Pancreatic transplantation in patients with diabetes can stabilize neuropathy and, in some instances, improve motor, sensory, and autonomic function.

Other treatments include off-label use of several drugs and devices. Drugs commonly prescribed to manage pain symptoms include tricyclic antidepressants (TCAs), selective serotonin reuptake inhibitors (SSRIs), and serotonin–norepinephrine reuptake inhibitors (SNRIs). Other treatment strategies such as acupuncture, transcutaneous electrical nerve stimulation (TENS), capsaicin patches and creams, topical anesthetics, and isosorbide dinitrate (ISDN) spray may also be used. Each of these can alleviate some of the pain symptoms. None demonstrate any ability to improve the underlying neuropathy.

